8.4 Visit 3, Month 12 (Final Trial Assessment)

Visit 3 will occur at an interval of 12 months (\pm four weeks) after the Baseline Visit and involve the following procedures:

- Administer QoL and functional capacity questionnaires.
- Record adverse events as reported by the participant or observed by the investigator.
- Confirm current rate control therapy (including dosage) and check concomitant medications.
- Assessment of compliance.
- Transthoracic echocardiography (as per **Section 9.6**), with images delivered to the echocardiographic core laboratory for blinded reporting.
- Collect blood sample for serum digoxin concentration, potassium and creatinine as part of standard clinical care.
- Record time in therapeutic range for patients on anticoagulation with vitamin-K antagonists and compliance in patients receiving non-VKA oral anticoagulants.
- Obtain a twelve lead ECG.
- Record the results of physical examinations and vital signs.
- Supervise a 6-minute walk test, recording distance walked and peak heart rate.
- Complete other CRF requirements.
- If an echocardiogram has been performed for clinical reasons since the previous visit, images will be retrieved and sent to the core echocardiographic laboratory.
- Complete the end of trial standardised letter to the GP and clinician explaining that the participant has reached the end of the trial protocol and is no longer bound by their allocated medication strategy. Advise that all participants are invited for continued follow up and long term clinical outcome assessment.
- Provide final instructions to participant (e.g. follow-up of ongoing adverse events).

8.5 Investigator-blinded Endpoints

Investigator-blinded endpoints (PROMs, echocardiography and biomarkers) will be assessed by the core laboratory, identified only by the trial number. Ambulatory ECG and serum digoxin level will remain unblinded and results delivered to the responsible clinician.

8.6 Long Term Follow-Up

In patients who have agreed to NHS data linkage, a follow-up CRF will be completed. The CRF will capture items that include, but are not limited to death, hospital admissions and cardiovascular events. The planned interval for outcome assessment is 2 and 5 years post-enrolment.

8.7 Withdrawal

Participants may withdraw at any time during the main **RATE-AF** trial if they choose not to continue or if their clinical team feel that continued participation in the trial is inappropriate.

An investigator may deem it necessary to withdraw a participant from the trial if:

- 1) Any clinical adverse event, laboratory abnormality, or other medical condition or situation occurs such that continued participation in the trial would not be in the best interest of the participant.
- 2) The participant meets an exclusion criterion (either newly developed or not previously recognised) that precludes further trial participation.

Full details of the reason(s) for withdrawal should be recorded on the Case Report Forms (CRFs) if healthcare professional-initiated, otherwise a simple statement reflecting patient preference will suffice.

Clear distinction will be made between withdrawals from trial treatments whilst allowing further follow-up, and any participants who refuse any follow-up. If a participant explicitly withdraws consent to any further data recording, then this decision will be respected. All communications surrounding the withdrawal will be noted in the participant's records and no further data will be collected for the participant.

In the case of missing echocardiographic outcome data due to withdrawal (but with consent for ongoing follow-up) or death, results of recent clinical echocardiography will be retrieved. The participant's permission to obtain such data will be obtained and documented during the consent process. As with all trial echocardiograms, the scan will be reported by the core echocardiographic laboratory. With respect to patient-reported outcomes, QoL questionnaires will be mailed to participants who withdraw from trial treatment but consent to ongoing follow up. Those patients where adverse symptoms were related to withdrawal will be invited to a focus group for further discussion.

8.8 Trial Duration

Patients will be on trial medication for 12 months and will be followed-up, during this period according to the protocol. At the end of the 12 months, the participants may, as determined by their clinician, continue on medication but it will not be considered part of the trial intervention. The trial will cease when the 12-month follow-up has been completed for the last participant recruited.

Table 1: Schedule of Assessments

Procedures		Baseline Visit	Up-titration Visits (Day 14 to 60)	Visit 2, Month 6 (± 4 weeks)	Visit 3, Month 12 (± 4 weeks)
Assessment of eligibility criteria		X			
Informed consent taken		X			
Review of medical history		X			
Review of medications		X	X	X	X
Physical exam	Complete	X			
	Symptom-directed		X	X	X
	Vital signs	X	X	X	X
Quality of life assessment		X	(X)	X	X
Functional and cognitive assessment		X		X	X
Transthoracic echocardiogram		X			X
12-lead electrocardiogram		X		X	X
6-minute walk test		X		X	X
24-hour ambulatory ECG			X	(X)	
Clinical labs	Chemistry	X		X	X
	Haematology	X		X	X
	Serum digoxin			(X)	(X)
Trial labs	BNP	X		X	X
	Stored sample	X		X	
Assessment of compliance			X	X	X
Assessment of adverse events			X	X	X

Parentheses denote where a procedure is dependent on the stage of participants within the trial.

9 Trial Procedures

9.1 Procedures Defined as Standard Clinical Care

The following assessments are considered part of the standard clinical care of AF patients receiving heart rate control therapy and will occur at all trial visits:

- Blood tests for haemoglobin, serum creatinine, potassium and serum digoxin concentration; these will be obtained by the research nurse and submitted to the site-specific hospital laboratory as per local guidelines and SOPs, ensuring that all specimens are accurately labelled and handled appropriately. In the case of results requiring urgent action, local policies will be followed which may include the participant visiting their GP, local hospital or investigator. In all cases, appropriate trial documentation will be completed.
- A 12-lead ECG; these will be completed by appropriately trained local staff.

9.2 Medical History

Medical history will be obtained by interview and from medical records (physical and electronic) at the Baseline Visit comprising:

- Cardiovascular history, including prior ischaemic coronary disease, interventions and surgery, history of hypertension, heart failure or hyperlipidaemia, stroke or transient ischaemic attack, pulmonary embolus/deep vein thrombosis and peripheral vascular disease.
- AF history, including year of diagnosis, previous cardioversions, previous ablation therapy and anti-arrhythmic drug history.
- Pacemaker history, including date and reason for implantation, type of device (single-chamber, dual-chamber, biventricular, implanted defibrillator) and dependency.
- Non-cardiac history, including diabetes mellitus, airways disease (asthma/COPD), renal impairment, bleeding history and other major co-morbidities.
- Social and demographic history, including smoking status (current/ex/never), race (Caucasian/Indian subcontinent/Asian/African/other) and physical activity using the International Physical Activity Questionnaire (short form).

9.3 Medication History

Medications history will be assessed according to the categories below and include current dosage. Except for anticoagulation, antiarrhythmic and rate control therapies, only current medications will be included.

- Anticoagulation therapy (vitamin-K antagonists and novel agents), including past use, INR results and time in therapeutic range.
- Antiarrhythmic therapy, including past use.
- Rate control therapy (beta-blockers, digoxin, CCB), including past use.

- Antiplatelet therapy.
- Angiotensin-converting enzyme inhibitors or angiotensin receptor blockers.
- Aldosterone antagonists.
- Diuretics (loop, thiazide, potassium-sparing, others).
- Nitrates.
- Other anti-hypertensive/anti-anginal therapy.
- Statins.
- Other lipid-lowering medication.
- Diabetic medication and insulin.
- Asthma/COPD medication (including inhalers).
- Non-steroidal anti-inflammatory agents.

9.4 Physical Examination

Physical and vital signs will be assessed at all up-titration and trial visits. In most cases, a targeted physical examination will be performed, comprising of cardiovascular elements as summarised below:

- Heart rate (manual palpation at radial artery and apex).
- Heart sounds.
- Lung auscultation.
- Assessment of jugular venous pressure and/or peripheral oedema.
- Other focused examinations according to symptoms and complaints.
- Blood pressure (two measurements at the right brachial in a seated position preferred, using a validated oscillometric device).
- Height (Baseline Visit only), weight (all listed visits) and waist circumference (Baseline Visit; defined as the narrowest point between ribs and hips when viewed from the front after exhaling to the nearest centimetre).

9.5 Patient Reported Outcomes

9.5.1 Choice of Outcomes and Qualitative Research

A systematic review (according to and in collaboration with the COnsensus-based Standards for the selection of health Measurement Instruments, COSMIN⁷⁴) is underway to evaluate PROMs in AF, with a focus on psychometric properties including internal consistency, reliability, and measurement error. Additional assessment and practical evaluation of PROMs will follow published guidance^{75, 76}, complementing qualitative research using patient focus groups, surveys

and directed interviews guided by the PROMs and qualitative research centres at the University of Birmingham.⁷⁷

Instruments for assessment will be selected on the basis of overall validity, preferably in this patient population but including other groups where data are limited. Patient focus groups will allow exploration of patient perspectives on appropriate instruments that adequately reflect the experience of living with AF.⁷⁸ They will also allow comparison of QoL questionnaires that adequately summarise patient-prioritised components of their health and well-being. Additional focus groups and individual interviews will occur at interim and final follow-up during the trial. These aim to understand the patient experience of trial participation and processes, including the ease of completion of QoL questionnaires, relevance, reasons for non-completion and other feasibility issues that emerge during the trial e.g. non-compliance and recruitment, with reference to core outcome sets for this population.⁷⁹ A patient and public involvement (PPI) panel will contribute to all stages in the focus group process.⁸⁰

This protocol was developed in accordance with the Standard Protocol Items for Randomized Trials [SPIRIT] statement⁸¹, and the latest PROM-specific guidance from the International Society for Quality of Life Research (ISOQOL) Best Practice taskforce.^{77, 82, 83}

9.5.2 Data Collection for PROMs

PROMs will be assessed at all main visits (Baseline, 2 and 3) and at the participants final up-titration visit (if applicable). The QoL tools used will be EQ-5D-5L, SF-36 and AFEQT. To avoid introducing co-intervention bias, all QoL data will be kept confidential and will not be used to inform clinical care.⁸⁴ Patients will be advised of this in the patient information sheet. PROMs will be collected at the start of each visit, before other trial procedures. In cases where the visit coincides with a clinician review, questionnaires should be completed in advance. The feasibility of using an online data collection tool will be explored, administered by trained research nurses and according to good-practice guidelines.⁸⁵ We will use this trial to perform an initial small-group assessment of electronic PROMs-equivalence to inform a future clinical event trial.

Qualitative research will be performed using a focus group of 10 volunteer patients enrolled at the start of the trial (5 in each randomised group). The focus group will meet after up-titration and then at 6 and 12 months. Detailed methods will be established before the first meeting, in collaboration with the University of Birmingham Qualitative Research Group.

All staff will receive training in QoL collection, with specific guidance on reducing introduced bias, minimising missing data and coaching participants to use the QoL software. Levels of missing PROMs data will be monitored. The site personnel responsible for collection of patient reported outcomes will be the Research Nurse under the supervision of the Principal Investigator.

9.5.3 Outcome Appraisal

Each QoL tool will be scored according to their published requirements (www.euroqol.org; www.sf-36.org; www.afegt.org), using total and sub-category scores where appropriate.

To avoid dilution of effect over time, the primary analysis will be at six months (adjusting for baseline QOL and stratification variables). We have predefined a focus on physical well-being, which we hypothesize are where the greatest treatment effects will be observed, but will explore all aspects of QoL. Exploratory analysis of medication effects over the 12-month period will also be analysed and remain clinically important, as little data currently exists on the longer-term profile of QoL in AF.

Qualitative research outcomes will focus on the clinical responsiveness of the QoL instruments. The findings of the COSMIN systematic report will determine these outcomes and their relevant appraisal.

The RATE-AF trial will allow us to gain an initial understanding and framework of the patient experience of AF. We aim to begin the process of determining appropriate and responsive PROMs for AF patients and the optimum methods for delivery into a subsequent large-scale clinical trial.

9.6 Transthoracic Echocardiography

Echocardiography will be performed at Visits 1 and 3 and focus on systolic left-ventricular (LV) function, diastolic function and left-atrial assessment. Images will be obtained by an accredited echocardiographer. All trial echocardiograms will be labelled with the Trial Number and pseudoanonymised patient data, with specific instruction that the echocardiographer will remain blinded to the treatment assignment. All images will be archived to the core echocardiographic laboratory, with a copy retained in the site file.

9.6.1 Reproducibility and Validity of Measurements

Inter-observer and intra-observer variability in measurement will be assessed by comparing results of the stated methods discussed below across the cardiac cycle. To evaluate the minimum number of repeat measurements required that maintains clinical utility, reproducibility of single measurements will be compared to averages of 3/5/10 beats. This will also include the reliability of using an 'index beat' with a cycle length equivalent to a heart rate of 70-80 beats per minute, or with similar preceding and pre-preceding RR intervals.

9.6.2 Systolic LV Function

Systolic LV function will be determined by the following methods:

- Two-dimensional biplane Simpson's method utilising the simultaneous multi-planar approach to obtain LVEF in a single heartbeat (four and two-chamber views). In each view, LV end-diastolic and end-systolic volumes (LVEDV, LVESV) are computed, with LVEF

calculated as $(LVEDV - LVESV) / LVEDV$. Two-dimensional echocardiography has excellent spatial resolution but is limited by potential foreshortening of the ventricular apex and drop-out of the endocardial border.

- Standard Simpson's biplane method with four and two-chamber volumes obtained from separate heartbeats. This is the conventional method in current clinical use but is limited by varying RR intervals in AF.
- Fractional shortening on M-mode along the minor-axis of the left-ventricle (parasternal long-axis), calculated by the formula: $(LV \text{ internal dimension in diastole} - LV \text{ internal dimension in systole}) / LV \text{ internal dimension in diastole}$. M-mode measurements are reproducible and easy to perform with excellent temporal resolution, but are limited in cases of regional wall motion abnormalities and in patients where the true minor-axis is difficult to visualise.
- Both automated endocardial tracking and speckle-tracking analysis will be utilised (where available) by the echocardiographic core laboratory. Multiple planes will be obtained (four-chamber, two-chamber and short-axis mid-ventricle views). These methods have the advantage of reducing operator time and are angle-independent, but rely on good ultrasound windowing. Global longitudinal systolic strain using 2D speckle-tracking has recently been proposed as an important marker for adverse cardiovascular outcomes in AF.⁸⁶
- Three-dimensional full-volume analyses of LV function, with single-beat analysis where feasible. This method has the advantage of not relying on geometric assumptions and allows the acquisition of full volume data within a single heartbeat. It correlates well with gold standard methods such as cardiac magnetic resonance imaging, but relies on adequate ultrasound windowing.
- Peak S-wave on tissue Doppler imaging (TDI) of the mitral valve annular sub-endocardium. This method has good correlation with LVEF across a wide range of function and is obtainable in patients with poor acoustic windows, but is limited in cases of regional wall motion abnormality.

Where poor quality acoustic windows limit accurate assessment of LV function, use of an intravenous contrast agent is recommended in participants without known allergy.

9.6.3 Diastolic LV Function

Diastolic LV function will be determined using the following methods (in all cases repeated over 3-5 cardiac cycles):

- Mitral inflow pulse-wave Doppler peak E velocity and deceleration time (DT).
- Mitral annular TDI to calculate septal E', lateral E' and the individual and averaged E/E' ratios.
- LV outflow tract pulse-wave Doppler to calculate isovolumic relaxation time (IVRT).
- Pulmonary vein pulse-wave Doppler to calculate peak systolic (where present) and diastolic velocities, ratio of peak velocities and DT of diastolic PV flow.

- Colour M-mode Doppler assessment of mitral flow propagation velocity (Vp) and ratio of E/Vp.

Overall diastolic function will be categorised according to the British Society of Echocardiography guidelines into normal function or mild/moderate/severe dysfunction based on a combination of the above variables. Individual parameters will also be categorised using cut-points identified from published studies.⁸⁷

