12.1.2 Secondary Outcomes

Patient-reported QoL:

- SF-36 global and domain-specific scores at 6 and 12 months
- EQ-5D-5L summary index and visual analogue scale at six and twelve months
- AFEQT overall score at six and twelve months

Cardiac function:

- Echocardiographic LVEF at 12 months
- Diastolic function (E/e' and composite of diastolic indices) at 12 months
- Functional assessment
- Six-minute walking distance at 6 and 12 months
- Change in European Heart Rhythm Association (EHRA) class at 6 and 12 months

Biomarkers:

- Change in B-type natriuretic peptide (BNP) levels at 6 months
- Change in heart rate using 24-hour ambulatory ECG

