- General Health Perception Score = ((GHP-5)/20)*100

AGPHYSICO

$(PF*0.456) + (RP*0.362) + (Pa*0.367) + (GHP*0.199) + (EV*-0.050) + (SF*-0.028) + (RE*-0.110) + (MH*-0.256)$

AGMENTCO

$(PF*-0.227) + (RP*-0.102) + (P*-0.130) + (GHP*0.036) + (EV*0.278) + (SF*0.272) + (RE*0.329) + (MH*0.460)$

Physical Component Summary score (PCS)

$((AGPHYSICO-82.261)/20.867)*10+50$

Mental Component Summary score (MCS)

$((\text{AGMENTCO}-63.7796)/19.582)*10)+50$

EQ-5D (5 level)

The current NICE guidelines (updated October 2019) on the use of EQ-5D-5L scoring based on the most recent value set for England published by Devlin et al. 2018 was not to use this and instead to map the 5L data into 3L value set based on mapping function developed by van Hout et al. 2012.

EQ-5D-5L have developed the crosswalk value sets for the 5L to 3L and so these values will be used for scoring: (<https://euroqol.org/eq-5d-instruments/eq-5d-5l-about/valuation-standard-value-sets/crosswalk-index-value-calculator/>).

For those patients that die prior to completing the EQ5D questionnaire, for the Index score a value of "0" will be imputed since for this questionnaire, a value of 0=death.

AFEQT questionnaire overall score

$$100 - \left[\frac{(\text{sum of severity for all questions answered} - \text{number of questions answered}) * 100}{\text{Total number of questions answered} * 6} \right]$$

*Note: ignore last two questions of the AFEQT questionnaire for scoring as they will be tabulated separately

IPAQ score (as continuous score)

- Sitting = N/A for IPAQ score
- Walking = 3.3 METs
- Moderate Intensity = 4.0 METs
- Vigorous Intensity = 8.0 METs

Total MET-minutes/week: MET level x minutes of activity/day x days per week

IPAQ score= Walk (3.3*min/day*days) + Moderate (4.0*min/day*days) + Vigorous (8.0*min/day*days)

NT-pro-BNP

Since this data is expected to be not normally distributed, a log transformation (natural log) for this data will need to be done to approximate normality prior to any analysis.

Composite of diastolic indices

This outcome will be coded as a binary yes/no, with "yes" representing patients that have a diastolic dysfunction present and "no" for patients that don't.

There is an algorithm to determine whether the patient has a diastolic function or not and it will be computed based on the following:

Does the patient have any **one** of the following diastolic parameters?

- Average E/e' (taken from lateral and septal wall) ≥ 15

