- **Change in European Heart Rhythm Association (EHRA) class at 6 and 12 months**

The data for this outcome is categorical in nature and in 5 orderly categories; 1=None, 2a=Mild, 2b=Moderate, 3=Severe, 4=Disabling. This data is collected as baseline, 6 months and 12 months. This data will be summarised as number and percentage by treatment arm and time-point with respect to the EHRA class.

The analysis for this outcome will be conducted using an ordinal logistic regression model, where the outcome will be the EHRA class at follow up (with EHRA class 1 being the reference category) and independent variables in the model being the baseline EHRA class, treatment arm, gender, age at randomisation and baseline LVEF. An adjusted odds ratio and 95% confidence interval will be estimated from the ordinal logistic regression.

Higher EHRA class is considered to be a worse outcome and since the Bisoprolol arm will be used as a reference category in the model, higher values will indicate worse outcome for Digoxin arm.

Note: separate analysis will be done for 6 month and 12 month time-point.

We will also code this outcome as a binary “yes/no” variable where “yes” will be determined if patients had a 2 class improvement in the EHRA class from baseline. The full details for the computation of this are described in the data manipulations section 9.4.

The analysis for this outcome will be conducted using a logistic regression model, where the outcome will be the computed binary variable “yes/no” (with yes being the reference category) and independent variables in the model being treatment arm, gender, age at randomisation and baseline LVEF. An adjusted odds ratio and 95% confidence interval will be estimated from the logistic regression model.

Since we are modelling whether patients had an improvement from baseline and that the Bisoprolol arm will be used as a reference category in the model, higher values will indicate better outcome for Digoxin arm.

Note: again separate analysis will be done for 6 month and 12 month time-point.

Biomarkers

- **Change in NTpro-B-type natriuretic peptide (NTpro-BNP) levels**

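### The protocol grades overall diastolic function in four classes; the SAP analyses the diastolic composite only as yes/no and has no analysis or table of the grade

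*Protocol*

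**What the plan says.** **Protocol.** The secondary outcome in 12.1.2 is "Diastolic function (E/e' and composite of diastolic indices) at 12 months". That list does not define the composite. Section 9.6.3 lists the echocardiographic variables and then says: "Overall diastolic function will be categorised according to the British Society of Echocardiography guidelines", giving four ordered classes, "into normal function or mild/moderate/severe dysfunction based on a combination of the above variables". It adds a second categorisation: "Individual parameters will also be categorised using cut-points identified from published studies".

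**SAP.** For the composite, 9.4 says: "This outcome will be coded as a binary yes/no", where *yes* means dysfunction is present. The rule has two steps:

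- Step 1: average E/e' of at least 15 is enough on its own.
- Step 2: otherwise, *yes* needs two or more of IVRT at most 65 ms, mitral E deceleration time at most 120 ms, average E/e' at least 11, and pulmonary vein diastolic deceleration time at most 220.

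Section 9.6 analyses the 12-month yes/no result by logistic regression, adjusted for the baseline category, minimisation variables, age and baseline LVEF. It analyses E/e' separately as a continuous, baseline-adjusted outcome. Appendix D6 has templates for E/e' and for the yes/no composite, and none for the four grades. The SAP does not explain how its composite relates to the grade.

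For EHRA class, which is also ordered, the SAP takes another course: "The analysis for this outcome will be conducted using an ordinal logistic regression model", with a binary version second.

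**The concern.** The protocol commits to an ordered grade for a domain that is a named secondary outcome, and the analysis plan then makes no use of it. A patient who moves from severe to mild dysfunction, or the reverse, may have the same composite value at baseline and at 12 months. If few patients have normal function at entry, most of the possible change lies within the dysfunction grades, where the composite cannot register it.

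The trial is also meant to supply planning data for a larger trial (Protocol 2.1), and SAP 4.4 lists population standard deviations and proportions for all outcomes among the feasibility outcomes. A yes/no coding provides no grade distribution for that purpose.

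**Working it through.** **The plan's own figure.** The documents give no sample size or power for the composite. The only stated calculation is for a continuous quality-of-life measure: n per arm = 2(1.960 + 1.036)² / 0.5² = 71.8, so 72 per arm and 144 in total; 144 / 0.90 = 160. Power with 72 per arm is 85.1%. This reproduces, but it does not bear on the composite.

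**The two definitions side by side.**

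| | Protocol 9.6.3 | SAP 9.4 |
|---|---|---|
| Result | normal, mild, moderate, severe | dysfunction yes or no |
| Source of rule | named guideline, content not reproduced | rule written out in the SAP |
| Variables | a combination from the full list | E/e', IVRT, E deceleration time, pulmonary vein diastolic deceleration time |
| Listed but unused in the SAP rule | – | pulmonary vein velocities and their ratio; "Colour M-mode Doppler assessment of mitral flow propagation velocity (Vp) and ratio of E/Vp" |
| Analysis or table in the SAP | none | logistic regression and D6 table |

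**What the coding hides.** Four grades allow 4 × 3 = 12 ordered changes. Those among mild, moderate and severe number 3 × 2 = 6, and a normal/any-dysfunction split shows none of them. The other 6 (3 to normal, 3 from normal) can appear, provided the SAP's *no* matches the protocol's *normal*.

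**What the other planned analysis recovers.** With the remaining indices outside their cut-offs, E/e' of 24 and E/e' of 16 are both *yes*, so a fall from 24 to 16 leaves the composite unchanged. The continuous E/e' analysis does see that fall. At E/e' of 14 only one step-2 criterion is met and the result becomes *no*, so the composite sees that change. By contrast, a patient with E/e' steady at 12 who goes from meeting all four step-2 criteria to meeting two stays *yes*, and E/e' does not move either. Neither planned analysis registers that change.

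**Size under assumed grade mixes.** Under proportional odds with 1:1 allocation, information is proportional to 1 − Σp³. For four grades this runs over all four proportions. For a split at normal proportion p it is 1 − p³ − (1 − p)³ = 3p(1 − p). The ratio is the share of information kept. Power uses SE(log OR) = √(12 / (N × information)), with N = 144 and an assumed common odds ratio of 2.5.

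| Assumed normal/mild/moderate/severe (%) | Four grades | Yes/no | Share kept | Power, four grades | Power, yes/no |
|---|---|---|---|---|---|
| 70/15/10/5 | 0.6525 | 0.63 | 97% | 73% | 71% |
| 50/20/20/10 | 0.858 | 0.75 | 87% | 84% | 79% |
| 40/30/20/10 | 0.90 | 0.72 | 80% | 85% | 77% |
| 25/25/25/25 | 0.9375 | 0.5625 | 60% | 87% | 66% |
| 15/35/30/20 | 0.91875 | 0.3825 | 42% | 86% | 50% |
| 10/30/40/20 | 0.90 | 0.27 | 30% | 85% | 38% |

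**Sensitivity to the cut.** The SAP rule need not fall at normal versus any dysfunction. For mixes 20/40/30/10, 30/30/25/15 and 50/25/15/10, a cut at normal keeps 0.48/0.90 = 53%, 0.63/0.927 = 68% and 0.75/0.855 = 88%. A cut between mild and moderate keeps 0.72/0.90 = 80%, 0.72/0.927 = 78% and 0.5625/0.855 = 66%. The order reverses, so no single figure can be attached to this trial.

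**The case against.** The best defence is that the protocol never equates the composite with the four-class grade. Section 9.6.3 also plans cut-points for individual parameters, and the SAP rule, which combines such cut-points, could be read as defining a composite the protocol left open. This stands as far as it goes: a reader might infer that the SAP replaced the protocol's outcome, and the documents do not prove that. Against it, 9.6.3 is the only place where the protocol combines the indices into one result, and its cut-point sentence concerns parameters one at a time. On either reading the grade has no planned analysis.

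A reader might also infer that change among patients with dysfunction goes unseen, or that diastolic function is reported only as a dichotomy. Neither is right. Recovery to *no* changes the composite, and continuous E/e' is the other half of the same named outcome.

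The unused variables show less than they seem to. The protocol speaks of a combination of the listed variables, not all of them, and the guideline rule is not in the documents, so its cut-offs cannot be compared with the SAP's.

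Two practical objections stand in part. SAP 9.7 could admit the grade as a descriptive summary, so it is formal analysis and a specified table that are missing. An ordinal model may also have sparse cells: with EHRA in five categories (SAP 9.1) and baseline grade in four, it has up to 1 + 3 + 1 + 4 + 1 + 1 = 11 coefficients for treatment, baseline grade, gender, EHRA, age and LVEF, plus three thresholds. The EHRA comparison is suggestive only, since EHRA class is itself the named outcome and is recorded on an ordered scale.

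**Conclusion.** The point holds in a limited form. The protocol commits to a four-class grade of overall diastolic function; the SAP analyses a yes/no composite by its own rule, has no model or table for the grade, and does not say how the two relate. What is lost is graded change in the combined measure, and change in indices other than E/e' that does not cross the SAP threshold.

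The size cannot be settled from the documents. The 30% to 97% range rests on assumed grade mixes, on proportional odds, and on the SAP cut coinciding with normal versus any dysfunction. The power figures further assume an odds ratio of 2.5 and 144 evaluable patients, which is the quality-of-life number and not an echocardiography number. The loss is small if most patients have normal function and large if few do. Entry requires breathlessness of NYHA class II or more, which makes a low normal share plausible but does not show it. The primary outcome is unaffected.

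**What to change.** Keep the yes/no composite and the continuous E/e' analysis as planned. Then:

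1. State in SAP 9.4 how the composite relates to the grade in Protocol 9.6.3, and why the yes/no form was chosen.
2. Add to Appendix D6 a table of the four grades by arm at baseline and 12 months.
3. Add to SAP 9.6 a supportive ordinal logistic model of the 12-month grade, adjusted for baseline grade, minimisation variables, age and baseline LVEF, with a stated rule for collapsing sparse grades. Label it supportive to the existing analyses.
4. If the grade is no longer assigned, amend Protocol 9.6.3 instead of steps 2 and 3.

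The new table should say that an odds ratio above 1 means worse function on digoxin. The D6 footnote under the yes/no composite reads the other way, although *yes* there means dysfunction, and should be checked at the same time.

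The cost is one table and one model. The grade is already required by the protocol, but neither document says who assigns it or sets out the rule, so the SAP must name both. The statistical price is one further secondary analysis in a plan that makes no multiplicity correction (SAP 5.2), with the possibility of sparse grades.
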